7.0 Participant Disposition

The number and percentage of participants in the two study populations (Safety and mITT) will be summarized by treatment group; the overall number of patients screened will be presented.

The number and percentage of participants who complete the study and of participants who prematurely discontinue the study will be presented for each treatment group and pooled across treatment groups for the mITT population. The reasons for premature discontinuation from the study as recorded on the termination pages of the electronic case report forms will be summarized (number and percentage) by treatment group for the mITT population. All

participants who prematurely discontinue during the study will be listed by discontinuation reason for the mITT population.

8.0 Demographics and Other Baseline Characteristics

Demographic parameters (age; age group; race; ethnicity; sex), baseline characteristics (weight; height; and body mass index, calculated as weight [kg]/(height [m])²), waist circumference (m), and other disease characteristics (type of surgery and number of grafts) will be summarized descriptively by treatment group for the safety population. Continuous variables will be summarized by number of participants and mean, SD, first quartile (Q1), median, minimum, third quartile (Q3), and maximum values. Categorical variables will be summarized by number and percentage of participants.

Medical history data will be coded using the Medical Dictionary for Regulatory Activities (MedDRA). The number and percentage of participants with medical history ongoing at screening will be summarized by system organ class, preferred term, and treatment group for the safety population. Data for medical history that is not ongoing at screening will be summarized and presented in a similar manner. An overall total will be provided for the study as well as by treatment group.

Prior medication is defined as any medication taken before the study treatment. Concomitant medication is defined as any medication taken on or after the day of study treatment.

Both prior and concomitant medications will be coded using the Anatomical-Therapeutic-Chemical classification text from World Health Organization (WHO) Drug Dictionary. The use of prior and concomitant medications will be summarized by the number and percentage of subjects in each treatment group for the safety population. If a participant took a specific medication multiple times or took multiple medications within a specific therapeutic class, that participant would be counted only once for the coded drug name or therapeutic class.

In addition to summarizing all medications as discussed above, a separate tabulation will also be provided for the following medications of interest:

- The following antiarrhythmics: quinidine, procainamide, disopyramide, mexiletine, flecainide, propafenone, amiodarone (including amiodarone hydrochloride, amiodarone hydrochloride w/ glucose and amiodarone;glucose), dronedarone, dofetilide, sotalol (including sotalol hydrochloride), and ibutilide.
- The following anticoagulants: warfarin (including warfarin sodium), dabigatran, apixaban, rivaroxaban, and edoxaban (including edoxaban tosilate).

Concurrent procedures will be presented in a listing. A tabulation will be provided for concurrent procedures performed due to atrial fibrillation or atrial flutter. Concurrent procedures performed

due to atrial fibrillation or atrial flutter may include: alcohol septal ablation, cardiac ablation, cardioversion, and additional cardiac surgery. See Section 10.3 below for additional discussion of concurrent procedures performed due to atrial fibrillation or atrial flutter.

Additional medications or concurrent procedures meeting the classifications above may be added at the discretion of the clinical team prior to the interim database lock for the primary analysis.

9.0 Extent of Exposure

All study participants will be treated only once on their day of surgery. Study treatment exposure data will be listed for the safety population.

Descriptive statistics of the study duration, calculated for each participant as the number of days from the date of the study treatment to the date the participant exits the study, will be presented by treatment group. In addition, the number and percentage of participants whose study duration belong to each of the following intervals will also be presented by treatment group: ≥ 6 days, ≥ 14 days, ≥ 30 days, ≥ 60 days, ≥ 90 days, ≥ 180 days ≥ 270 days, ≥ 360 days. These summaries will be based on the safety population.

10.0 Efficacy Analyses

All efficacy analyses will be based on the mITT Population, unless otherwise specified. Note that the use of the phrase "AF" or "AF episode" in the section and subsections below implies an occurrence of either atrial fibrillation or atrial flutter. Other analyses will be conducted to assess only atrial fibrillation, only atrial flutter, only atrial tachycardia, and a combination of either atrial fibrillation, atrial flutter, or atrial tachycardia.

Each participant will be continuously monitored for the first 30 days post-surgery, and during the first 7 days following Day 60, Day 90, Day 180, Day 270, and Day 360 visits, for all occurrences of AF episodes as well as the length of time spent in each of the corresponding AF episodes using ECG patches (ePatch) placed on the participant's chest.

Even though each participant is expected to wear the epatch for the first 30 days post-surgery, and during the first 7 days following Day 60, Day 90, Day 180, Day 270 and Day 360 visits, all analyzable data (interpretable) collected from the epatch will be included in the analysis regardless of any deviations from these timeframes.

The ECG measurements collected for AF episodes post-surgery will be used to provide 10 different definitions for POAF for use in statistical analyses, namely:

- 1. at least 1 continuous AF episode \geq 30 seconds
- 2. at least 1 continuous AF episode \geq 2 minutes

- 3. at least 1 continuous AF episode \geq 5 minutes
- 4. at least 1 continuous AF episode ≥ 6 minutes
- 5. at least 1 continuous AF episode \geq 30 minutes
- 6. at least 1 continuous AF episode \geq 1 hour
- 7. at least 1 continuous AF episode \geq 4 hours
- 8. at least 1 continuous AF episode ≥ 6 hours
- 9. at least 1 continuous AF episode \geq 12 hours
- 10. at least 1 continuous AF episode \geq 24 hours

Based on information collected from continuous monitoring for all occurrences of AF during the first 30 days post-surgery, the percent of time spent in AF (hereinafter referred to as AF Burden) during the first 30 days post-surgery will be calculated as (the total time spent in AF during the first 30 days post-surgery divided by the total time of analyzable data obtained from the ECG patch during the first 30 days post- surgery) multiplied by 100.

In addition, similar definitions of POAF as well as the derivation of the AF Burden will be obtained based on continuous monitoring of all occurrences of AF during the first 7 days following Day 60, Day 90, Day 180, Day 270, and Day 360 visits.

All analyses using ECG patch data will be based on observed data; no imputation will be performed on missing data from the ECG patch device. Descriptive statistics of the total time of analyzable data obtained from the ECG patch during the first 30 days post- surgery will be presented by treatment group. Similar statistics will be presented for each of the first 7 days following Day 60, Day 90, Day 180, Day 270, and Day 360 visits.

Unless otherwise stated, the ICU admission date for the index surgery (initial care of indication under study) will be used as reference timepoint to establish if an event occurred within a specified timeframe "post-surgery". For example, the occurrence of AF during the first 30 days post-surgery will imply the occurrence of AF during the first 30 days following the initial ICU admission date.

In general, continuous and ordinal variables will be summarized by descriptive statistics and will include sample size, mean, standard deviation, median, minimum, and maximum. Nominal variables will be summarized by frequency and percentage.

Inferential analyses will include 3 treatment groups: Placebo, 125 U, and 250 U of AGN-151607. Each dose level of AGN-151607 (125 U and 250 U) will be separately compared to placebo. All treatment comparisons will be made at the $\alpha = 0.05$ level (2-sided). To control for multiplicity in comparing 2 doses of AGN-151607 with placebo, the primary efficacy variable will be tested sequentially by first comparing the high dose to placebo. The low dose will be compared to

placebo only if the comparison to the high dose is found to be statistically significant. There will be no adjustment for multiple comparisons for all other efficacy variables.

Mis-stratified participants, if any, will be analyzed based on the correct stratification group [type of surgery (presence or absence of valve surgery) and age group (< 65 or ≥ 65 years)], not the stratification group to which the participants were assigned at the time of randomization.

Unless otherwise stated, the use of the phrase "percentage of participants" for any efficacy variable in the sections below assumes the variable is a binary categorical response outcome.

10.1 Primary Efficacy Variable

For primary efficacy consideration, POAF will be defined as any continuous episode of AF lasting 30 seconds or more during the first 30 days post-surgery. The primary efficacy variable is the percentage of participants with at least 1 continuous AF episode \geq 30 seconds during the first 30 days post-surgery.

For each of the AGN-151607 doses of 125 U and 250 U, the null hypothesis is that there is no difference between that dose group and placebo in the percentage of participants with at least 1 continuous AF episode \geq 30 seconds during the first 30 days post-surgery. The alternative hypothesis is that there is a difference between the AGN-151607 dose group under consideration and placebo.

The proportion of participants with at least 1 continuous AF episode \geq 30 seconds during the first 30 days post-surgery will be presented for each treatment group. Between-group comparisons will be performed using the Cochran-Mantel-Haenszel (CMH) test for general association stratified by type of surgery (presence or absence of valve surgery) and age group (< 65 or \geq 65 years). P-values, adjusted Mantel-Haenszel (MH) odds ratios and relative risks (and their corresponding 95% confidence intervals) will be presented for each comparison of AGN-151607 versus placebo. Exact (Clopper-Pearson) 95% confidence intervals of the observed proportion will be presented for each treatment group. In addition, exact unconditional 95% confidence interval (using the score method) for the difference in observed proportion between each AGN-151607 dose group versus placebo will also be presented.

For the primary efficacy variable, supplementary analyses will be performed based on the Supplementary ePatch Analysis Sets (SEA-7 and SEA-30) and the Beta Blocking Agent Withdrawn ePatch Analysis Set. The supplementary analyses will use the same methods described for the primary analysis.

For the primary efficacy variable, subgroup analyses will be performed using the same methods described for the primary analysis based on the correct stratification group (with the other stratification factor used for the stratified CMH test):

- type of surgery (presence or absence of valve surgery)
- age group (< 65 or \geq 65 years)]

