# 6.3. Measures to Minimize Bias: Randomization and Blinding

At screening, each participant who provides informed consent will be assigned a number that will serve as the participant identification number on all study documents.

An automated Interactive Web Response System (IWRS) assigns the participant's identification number and this will be used to manage the randomization and intervention assignment based on a centralized randomization list prepared by Allergan Biostatistics. The randomization will be stratified by age ( $< 65, \ge 65$  years) and type of surgery (presence/absence of valve surgery). Within each stratification group, participants will be randomly assigned to one of the intervention groups in a 1:1:1 ratio. Before the study is initiated, the log-in information and instructions for the IWRS will be provided to each site.

Investigators will remain blinded to each participant's assigned study intervention throughout the course of the study.

At each study site, a designated staff member will serve as the independent drug reconstitutor (IDR). This person will be responsible for study intervention preparation.

The IDR will prepare the study intervention as described in the Pharmacy Manual. The investigator will inject the reconstituted study intervention according to the study intervention

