4.0 Introduction

This statistical analysis plan (SAP) provides a detailed elaboration of the statistical analyses of the efficacy and safety data as specified in the final protocol of Study 1925-201-008 (amendment 1 version dated 25 September 2020). Specifications of tables, figures, and data listings are contained in a separate document.

This is a phase 2, multi-center, randomized, double-blind, placebo-controlled, dose-ranging study in patients 55-90 years of age who are scheduled to undergo open-chest cardiac surgery.

The length of this study will be 367 days, not including the screening visit, which may occur up to 28 days before the first study day (randomization). Signed informed consent from the participant will be obtained before any study-related procedures are begun. Patients meeting the inclusion/exclusion criteria will be randomized (1:1:1 ratio) to one of three treatment arms at the end of the screening period. Primary and secondary efficacy assessments will be assessed for 30 days post-surgery. Additional efficacy and exploratory assessments will be assessed through Day 367 post-surgery. All participants will be followed through Day 367 for safety assessments. Every attempt will be made for participants who prematurely discontinue from the study, regardless of cause, to be seen for a final evaluation.

The study schema is presented below.

D = study day; TC = telephone call; U = units; V = Visit

a Hospital discharge could take more than 6 days.

The schedule of evaluations is presented in the Table 4–1 below.

Page 7

Table 4–1Schedule of Evaluations: Study 1925-201-008

Study Period	Screening ^a	Days 1 to 60						Day 61 through Day 360								
Visit Number	V1	V2	V3	V4 ^b	V5 ^b	V6 ^b	V7 ^b	TC1	V8	V9	V10	V11	V12	V13	TC2	Early
Day Number	(up to 28 days)	D1	D2	D3	D4	D5	D6	D14	D30	D60	D90	D180	D270	D360	D367 ^d	Disc
Visit Windows	-	-	-	-	-	-	-	± 3d	± 3d	± 3d	± 7d	± 7d	± 7d	± 7d	V13 + 7d (+ 7d)	-
Informed consent	Х															
Inclusion and exclusion criteria	Xe	Х														
Demography	Х															
Physical examination	Х								Х					Xf		Х
Medical history	X															
Urine pregnancy test (for women of childbearing potential) ^{e,g}	Х	x														
Laboratory assessments ^{e,h}	Х	Х					Х		Х	Xi	Xi			Xi		Х
Sample collection for biomarker assessment ^e		Х	х	Х	Х											
12-lead ECG ^j	Х	Х	Х	Х	Х	Х	Х		Х	Xk	Xk	Xk	Xk	Xk		Х
ECG patch		Х	Х	Х	Х	Х	Х	Х	X ¹	X ^m	Х					
Vital signs ^{e,n}	Х	Х	Х	Х	Х	Х	Х		Х	Х	Х	Х	Х	Х		Х

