13.0 Determination of Sample Size

A sample size of 100 randomized participants per treatment group will provide approximately 80% power to detect the treatment difference between each of the AGN-151607 doses (assumed equally effective) and placebo for the primary efficacy endpoint. The power calculations are based on the following assumptions:

- The expected incidence of early postoperative AF within 30 days post-surgery will be 47.8% in the placebo group and 27.8% in each of the AGN-151607 groups. This assumption is based on the results observed in the Pokushalov study (Pokushalov 2015) and the Duke University Medical Center clinical trial (Waldron et. al., 2019).
- Two-sided Mantel-Haenszel test statistic and a significance level of 0.05 for the test.

Calculations were performed using commercial software PASS 2008 (Hintze 2008). Assuming that approximately 10% in each intervention group will drop out early from the study, a total of approximately 330 participants will be randomly assigned to study intervention, in order to have approximately 300 participants complete all the efficacy assessments up to Day 60 visit.

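### The primary risk difference has only an unstratified exact interval beside a stratified test: valid, but a few percent wider than needed and, in borderline results, able to disagree with the p-value

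*SAP*

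**What the plan says.** Protocol 6.3: "The randomization will be stratified by age" and by presence or absence of valve surgery, which makes four cells. SAP 10.1 carries both factors into the primary test: "Between-group comparisons will be performed using the Cochran-Mantel-Haenszel (CMH) test for general association stratified by type of surgery" and age group. The Mantel-Haenszel odds ratio and relative risk are adjusted in the same way.

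The risk difference is handled differently. SAP 10.1 gives each arm's proportion a Clopper-Pearson interval, then adds an "exact unconditional 95% confidence interval (using the score method) for the difference in observed proportion between each AGN-151607 dose group versus placebo". No strata are stated for it, and neither document supplies a stratified risk-difference interval elsewhere.

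Protocol 9.4.1.2 has the same mismatch, pairing a stratified CMH test with a normal-approximation interval for the difference. SAP 16.0, which lists changes from the protocol, does not mention the move to the exact method. SAP 10.2 applies the primary method to the binary secondary variables (14 by count), and SAP 10.3 applies it to further binary variables.

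**The concern.** Protocol 9.4.1.2 and SAP 10.2 both call surgery type and age group baseline risk factors for post-operative atrial fibrillation (POAF). If they are, the stratified design removes some between-stratum variance that a crude interval puts back. The exact unconditional method then adds conservatism of its own.

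The absolute difference is the natural effect measure here. The null hypothesis in SAP 10.1 concerns a difference in percentages, and the sample size rests on "47.8% in the placebo group and 27.8% in each of the AGN-151607 groups". SAP 12.0 says the interim analysis serves planning of later studies, for which the difference and its precision are direct inputs. Yet it is the one comparative estimate left unadjusted. At stake are a little precision and the chance that one table shows a significant p-value, an odds ratio interval excluding 1 and a risk-difference interval including 0.

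**Working it through.** **Inputs from the documents.** "A sample size of 100 randomized participants per treatment group will provide approximately 80% power"; event rates 47.8% and 27.8%; "Two-sided Mantel-Haenszel test statistic and a significance level of 0.05 for the test"; "randomized (1:1:1 ratio) to one of three treatment arms"; four strata. Stratum sizes and stratum event rates are not given, so they are assumed below and varied.

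**1. The plan's own figure.** Pooled rate (0.478 + 0.278)/2 = 0.378. Null SD √(2 × 0.378 × 0.622) = 0.686. Alternative SD √(0.478 × 0.522 + 0.278 × 0.722) = √0.4502 = 0.671.
- Without continuity correction: Φ[(0.20 × 10 − 1.96 × 0.686)/0.671] = 83.6%.
- With it (0.20 reduced by 1/100): 79.6%.

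The stated 80% reproduces with the correction. It concerns the test, not the interval.

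**2. Width due to ignoring the strata.** For balanced cells with weights w, per-arm variance is Σ w p(1−p) with strata and p(1−p) without. The normal-approximation 95% width at 100 per arm is 3.92 × √(variance sum/100).
- Crude: 3.92 × √(0.4502/100) = 0.263.
- Assumed cells of 20, 20, 30, 30 per arm and a common odds ratio for treatment. With a 20-point gradient, placebo is 25.8, 45.8, 45.8, 65.8% and active 12.0, 24.9, 24.9, 43.1%. Variance sum 0.230 + 0.188 = 0.418; width 0.254; ratio 0.254/0.263 = 0.964.
- 10-point gradient: width 0.261, ratio 0.991. Flat strata: ratio 1.000.
- Alternative assumption of 50% valve surgery and 65% aged 65 or over: the crude standard error is 0.9%, 2.5% and 5.9% larger when each factor carries an odds ratio of 1.5, 2 and 3.

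The range is therefore about 0% to 6%.

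**3. Width due to the exact method.** Exact limits invert two one-sided 0.025 score tests, maximised over the nuisance rate. Differences are placebo minus active; the comparator is the crude asymptotic score interval.

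| Data | Exact | Asymptotic score | Ratio of widths |
|---|---|---|---|
| 48/100 vs 28/100 | 0.055 to 0.330 (0.275) | 0.066 to 0.328 (0.262) | 1.05 |
| 53/110 vs 31/110 | width 0.260 | width 0.250 | 1.04 |
| 48/100 vs 35/100 | −0.008 to 0.265 (0.273) | −0.007 to 0.262 (0.269) | 1.01 |

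One caveat on the first row: the maximised tail probability is not monotone in the trial difference. It is 0.0259 at 0.048, 0.0202 at 0.053, 0.0242 at 0.055 and 0.0265 at 0.056. A rule taking the outermost value not rejected would give 0.048 as the limit, and 0.282/0.262 = 1.08.

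**4. A conflict shown.** Assumed counts in cells of 20, 20, 30, 30: placebo 4, 9, 14, 21 (48/100) and active 2, 5, 10, 18 (35/100).
- CMH: Σ(a − E) = 1 + 2 + 2 + 1.5 = 6.5. Σ variance = 1.308 + 2.333 + 3.661 + 3.470 = 10.772. χ² = 42.25/10.772 = 3.92, p = 0.048. The Mantel-Haenszel odds ratio interval is 0.29 to 0.99.
- Planned exact interval: −0.008 to 0.265, including 0 (one-sided exact p at zero 0.033, above 0.025).
- Stratified score interval with Mantel-Haenszel weights: 0.001 to 0.256, excluding 0.
- Mantel-Haenszel-weighted Wald: 0.004 to 0.256. Sato variance: −0.001 to 0.261, which still includes 0.

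The crude test gives p = 0.062 without any exact method, so here the strata cause the conflict.

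**5. How often.** 100,000 simulated trials per setting with the gradients of step 2, counting CMH p < 0.05 with an exact interval that includes 0:
- 20-point effect: 0.2% (flat) to 2.0% (20-point gradient).
- 14-point effect: 0.7% to 3.3%.
- No effect: 0.9% to 1.5%.

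The reverse conflict occurred in at most 0.2%.

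**The case against.** No decision rests on this interval. The test, the high-dose-then-low-dose sequence and alpha all depend on the CMH p-value, and SAP 10.1 already gives stratified odds ratios and relative risks with intervals. The interval also describes what it says it does. Under stratified 1:1:1 randomisation the crude difference is a valid estimate of the marginal difference, and an exact method errs towards over-coverage. All of this stands. A reader might infer that the primary test is compromised or the interval wrong; the documents support neither.

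A reader might also put the extra width down to the strata alone. That does not hold. At weak or moderate gradients (odds ratio 1.5 to 2, 0.9% to 2.5%) the exact method can contribute as much or more, and an unstratified asymptotic score interval would recover that part. The 6% end needs an odds ratio of about 3 per factor, roughly 20% POAF in younger non-valve placebo patients against 70% in older valve patients. The documents name the factors as risk factors but give no strength.

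Finally, replacing the exact interval on every binary endpoint would reach some that may be sparse over four strata: episodes of 24 hours or more, flutter alone, procedural interventions and the beta-blocker-withdrawn set. The stratified score interval was not tested there, and an exact interval is most defensible there. This limits the fix.

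The objection does not explain why the absolute effect alone should omit factors used in the randomisation and in every other primary comparison. With balanced cells the weighted and crude differences coincide (0.13 in the example), so stratifying barely moves the target.

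**Conclusion.** The point holds as one of precision and coherent reporting. The planned interval is valid but conservative. Ignoring the strata adds about 0% to 6% to its width. The exact method adds a separate 1% to 5% in the cases worked, or about 8% in one of them if the outermost exact limit is taken. A significant CMH test beside an interval including 0 arises in about 0.2% to 3% of trials, always near the significance boundary and almost always in that direction.

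These sizes rest on assumed stratum sizes and gradients; if the strata are not prognostic, the strata component is nil. Type I error and power of the primary test are unaffected. Nor should a reader infer that stratifying guarantees agreement: in the worked example the Sato interval still includes 0 while CMH gives p = 0.048.

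**What to change.** In SAP 10.1, report as the main absolute effect a Mantel-Haenszel-weighted risk difference with a stratified score 95% confidence interval, using the same four strata as the CMH test. Keep the exact crude interval as supportive, and retain it for binary endpoints or subsets where the strata are sparse. In SAP 16.0, list the change from the protocol's normal-approximation interval.

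The cost is a sentence or two in the SAP and a standard software option, with no new data. Disagreement with the CMH p-value will be less frequent, not eliminated.
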